11.1.3 Methods for Evaluation of Measurable Disease

All measurements should be taken and recorded in metric notation using a ruler or calipers. All baseline evaluations should be performed as closely as possible to the beginning of treatment and never more than 4 weeks before the beginning of the treatment.

The same method of assessment and the same technique should be used to characterize each identified and reported lesion at baseline and during follow-up. Imaging-based evaluation is preferred to evaluation by clinical examination unless the lesion(s) being followed cannot be imaged but are assessable by clinical exam.

Clinical lesions Clinical lesions will only be considered measurable when they are superficial (e.g., skin nodules and palpable lymph nodes) and ≥ 10 mm diameter as assessed using calipers (e.g., skin nodules). In the case of skin lesions, documentation by color photography, including a ruler to estimate the size of the lesion, is recommended.

Chest x-ray Lesions on chest x-ray are acceptable as measurable lesions when they are clearly defined and surrounded by aerated lung. However, CT is preferable.

Conventional CT and MRI This guideline has defined measurability of lesions on CT scan based on the assumption that CT slice thickness is 5 mm or less. If CT scans have slice thickness greater than 5 mm, the minimum size for a measurable lesion should be twice the slice thickness. MRI is also acceptable in certain situations (e.g. for body scans).

Use of MRI remains a complex issue. MRI has excellent contrast, spatial, and temporal resolution; however, there are many image acquisition variables involved in MRI, which

greatly impact image quality, lesion conspicuity, and measurement. Furthermore, the availability of MRI is variable globally. As with CT, if an MRI is performed, the technical specifications of the scanning sequences used should be optimized for the evaluation of the type and site of disease. Furthermore, as with CT, the modality used at follow-up should be the same as was used at baseline and the lesions should be measured/assessed on the same pulse sequence. It is beyond the scope of the RECIST guidelines to prescribe specific MRI pulse sequence parameters for all scanners, body parts, and diseases. Ideally, the same type of scanner should be used and the image acquisition protocol should be followed as closely as possible to prior scans. Body scans should be performed with breath-hold scanning techniques, if possible.

PET-CT At present, the low dose or attenuation correction CT portion of a combined PET-CT is not always of optimal diagnostic CT quality for use with RECIST measurements. However, if the site can document that the CT performed as part of a PET-CT is of identical diagnostic quality to a diagnostic CT (with IV and oral contrast), then the CT portion of the PET-CT can be used for RECIST measurements and can be used interchangeably with conventional CT in accurately measuring cancer lesions over time. Note, however, that the PET portion of the CT introduces additional data which may bias an investigator if it is not routinely or serially performed.

Ultrasound Ultrasound is not useful in assessment of lesion size and should not be used as a method of measurement. Ultrasound examinations cannot be reproduced in their entirety for independent review at a later date and, because they are operator dependent, it cannot be guaranteed that the same technique and measurements will be taken from one assessment to the next. If new lesions are identified by ultrasound in the course of the study, confirmation by CT or MRI is advised. If there is concern about radiation exposure at CT, MRI may be used instead of CT in selected instances.

Endoscopy, Laparoscopy The utilization of these techniques for objective tumor evaluation is not advised. However, such techniques may be useful to confirm complete pathological response when biopsies are obtained or to determine relapse in trials where recurrence following complete response (CR) or surgical resection is an endpoint.

Tumor markers Tumor markers alone cannot be used to assess response. If markers are initially above the upper normal limit, they must normalize for a patient to be considered in complete clinical response. Specific guidelines for both CA-125 response (in recurrent ovarian cancer) and PSA response (in recurrent prostate cancer) have been published [JNCI 96:487-488, 2004; J Clin Oncol 17, 3461-3467, 1999; J Clin Oncol 26:1148-1159, 2008]. In addition, the Gynecologic Cancer Intergroup has developed CA-125 progression criteria which are to be integrated with objective tumor assessment for use in first-line trials in ovarian cancer [JNCI 92:1534-1535, 2000].

Cytology, Histology These techniques can be used to differentiate between partial responses (PR) and complete responses (CR) in rare cases (e.g., residual lesions in tumor types, such as germ cell tumors, where known residual benign tumors can remain).

The cytological confirmation of the neoplastic origin of any effusion that appears or worsens during treatment when the measurable tumor has met criteria for response or stable disease is mandatory to differentiate between response or stable disease (an effusion may be a side effect of the treatment) and progressive disease.

FDG-PET While FDG-PET response assessments need additional study, it is sometimes reasonable to incorporate the use of FDG-PET scanning to complement CT scanning in assessment of progression (particularly possible 'new' disease). New lesions on the basis of FDG-PET imaging can be identified according to the following algorithm:

- a. Negative FDG-PET at baseline, with a positive FDG-PET at follow-up is a sign of PD based on a new lesion.
- b. No FDG-PET at baseline and a positive FDG-PET at follow-up: If the positive FDG-PET at follow-up corresponds to a new site of disease confirmed by CT, this is PD. If the positive FDG-PET at follow-up is not confirmed as a new site of disease on CT, additional follow-up CT scans are needed to determine if there is truly progression occurring at that site (if so, the date of PD will be the date of the initial abnormal FDG-PET scan). If the positive FDG-PET at follow-up corresponds to a pre-existing site of disease on CT that is not progressing on the basis of the anatomic images, this is not PD.
- c. FDG-PET may be used to upgrade a response to a CR in a manner similar to a biopsy in cases where a residual radiographic abnormality is thought to represent fibrosis or scarring. The use of FDG-PET in this circumstance should be prospectively described in the protocol and supported by disease-specific medical literature for the indication. However, it must be acknowledged that both approaches may lead to false positive CR due to limitations of FDG-PET and biopsy resolution/sensitivity.

Note: A 'positive' FDG-PET scan lesion means one which is FDG avid with an uptake greater than twice that of the surrounding tissue on the attenuation corrected image.

11.1.4 Response Criteria

11.1.4.1. Evaluation of Target Lesions

Complete Response (CR): Disappearance of all target lesions. Any pathological lymph nodes (whether target or non-target) must have reduction in short axis to <10 mm.

Partial Response (PR): At least a 30% decrease in the sum of the diameters of target lesions, taking as reference the baseline sum diameters.

Progressive Disease (PD): At least a 20% increase in the sum of the diameters of target lesions, taking as reference the smallest sum on study (this includes the baseline sum if that is the smallest on study). In addition to the relative increase of 20%, the sum must also demonstrate an absolute increase of at least 5 mm. (Note: the appearance of one or more new lesions is also considered progression).

Stable Disease (SD): Neither sufficient shrinkage to qualify for PR nor sufficient increase to qualify for PD, taking as reference the smallest sum diameters while on study.

11.1.4.2. Evaluation of Non-Target Lesions

Complete Response (CR): Disappearance of all non-target lesions and normalization of tumor marker level. All lymph nodes must be non-pathological in size (<10 mm short axis).

Note: If tumor markers are initially above the upper normal limit, they must normalize for a patient to be considered in complete clinical response.

Non-CR/Non-PD: Persistence of one or more non-target lesion(s) and/or maintenance of tumor marker level above the normal limits.

Progressive Disease (PD): Appearance of one or more new lesions and/or *unequivocal progression* of existing non-target lesions. *Unequivocal progression* should not normally trump target lesion status. It must be representative of overall disease status change, not a single lesion increase.

Although a clear progression of “non-target” lesions only is exceptional, the opinion of the treating physician should prevail in such circumstances, and the progression status should be confirmed at a later time by the review panel (or Principal Investigator).

11.1.4.3. Evaluation of Best Overall Response

The best overall response is the best response recorded from the start of the treatment until disease progression/recurrence (taking as reference for progressive disease the smallest measurements recorded since the treatment started). The patient's best response assignment will depend on the achievement of both measurement and confirmation criteria.

For Patients with Measurable Disease (*i.e.*, Target Disease)

Target Lesions	Non-Target Lesions	New Lesions	Overall Response	Best Overall Response when Confirmation is Required*
CR	CR	No	CR	≥ 4 wks. Confirmation**
CR	Non-CR/Non-PD	No	PR	
CR	Not evaluated	No	PR	
PR	Non-CR/Non-PD/not evaluated	No	PR	≥ 4 wks. Confirmation**
SD	Non-CR/Non-	No	SD	Documented at least once ≥ 4

	PD/not evaluated			wks. from baseline**
PD	Any	Yes or No	PD	no prior SD, PR or CR
Any	PD***	Yes or No	PD	
Any	Any	Yes	PD	

* See RECIST 1.1 manuscript for further details on what is evidence of a new lesion.
 ** Only for non-randomized trials with response as primary endpoint.
 *** In exceptional circumstances, unequivocal progression in non-target lesions may be accepted as disease progression.

Note: Patients with a global deterioration of health status requiring discontinuation of treatment without objective evidence of disease progression at that time should be reported as “*symptomatic deterioration*.” Every effort should be made to document the objective progression even after discontinuation of treatment.

For Patients with Non-Measurable Disease (i.e., Non-Target Disease)

Non-Target Lesions	New Lesions	Overall Response
CR	No	CR
Non-CR/non-PD	No	Non-CR/non-PD*
Not all evaluated	No	not evaluated
Unequivocal PD	Yes or No	PD
Any	Yes	PD

* ‘Non-CR/non-PD’ is preferred over ‘stable disease’ for non-target disease since SD is increasingly used as an endpoint for assessment of efficacy in some trials so to assign this category when no lesions can be measured is not advised

11.1.5 Duration of Response

Duration of overall response: The duration of overall response is measured from the time measurement criteria are met for CR or PR (whichever is first recorded) until the first date that recurrent or progressive disease is objectively documented (taking as reference for progressive disease the smallest measurements recorded since the treatment started).

The duration of overall CR is measured from the time measurement criteria are first met for CR until the first date that progressive disease is objectively documented.

Duration of stable disease: Stable disease is measured from the start of the treatment until the criteria for progression are met, taking as reference the smallest measurements recorded since the treatment started, including the baseline measurements.

11.1.6 Progression-Free Survival

PFS is defined as the duration of time from start of treatment to time of progression or death, whichever occurs first.

11.1.7 Response Review

All responses will be reviewed by an expert(s) independent of the study at the study's completion. Simultaneous review of the patients' files and radiological images will occur.

12. STATISTICAL CONSIDERATIONS

12.1 Study Design/Endpoints

With the advent of genomic profiling and targeted therapies, focusing on patients with a specific target (or genomic alteration) of interest regardless of disease type or histology is a new paradigm that cancer research is beginning to adopt. This is a Phase-2, "basket" study for patients with advanced cancers (stage 4, any histology) who have disease progression with at least one prior regimen, identified with predefined genomic alterations. Two separate cohorts will be accrued in parallel, defined by genomic *FGFR*, as well as *KIT*, *PDGFR α* , *ABL1*, *RET*, and *FLT3* alterations.

Cohort A will consist of patients identified with activating mutations or fusions in *FGFR* as well as patients with *FGFR* amplifications.

Cohort B will consist of patients identified with rare gene targets (*KIT*, *PDGFR α* , *RET*, *ABL1*, and *FLT3* alterations) for whom there may be downstream targeting and efficacy associated with ponatinib.

Our goal is to assess efficacy outcomes in these two cohorts when treated with ponatinib.

(a) Definition of primary outcome/endpoint:

The primary endpoint for each of the cohort in this study is overall response. Overall response is defined as the number of patients who achieve any response in the first 6 cycles of treatment. All eligible patients, selected by a CLIA approved assay, who have received at least one dose of ponatinib will be evaluable for response. Response for tumors would be assessed using the RECIST 1.1 criteria (using CT scans or calipers by clinical exam) where response will be defined as a partial or complete response.

(b) Definition of secondary outcomes/endpoints:

- Toxicity is defined as adverse events that are classified as either possibly, probably, or definitely related to study treatment per NCI CTCAE v4.0
- Overall survival is defined as the time from treatment initiation to death.
- Progression-free survival defined as the time from treatment initiation to progression or death

12.2 Analysis of Primary Objectives

Cohort A: *FGFR* mutations, fusions or amplifications

This cohort will utilize a two-stage Simon minimax phase II study design. In the relapsed/refractory setting for the multiple eligible disease types who have an *FGFR* mutation, fusion or amplification given the targeted nature of this regimen and preliminary data that support its use in those with *FGFR* mutations, fusions or amplifications, a true ORR of at least 20% would be considered promising in this patient population. Therefore, this study is designed to detect an ORR of at least 20% vs. the null hypothesis that the true ORR is at most 5%, representing a response by chance alone. Based on preclinical data, we expect that those with *FGFR* amplification may not be as susceptible to the targeting effects of ponatinib as those with *FGFR* mutation/fusions. We also expect that those patients identified with *FGFR* amplifications will be much more prevalent than those identified with *FGFR* mutations/fusions. To accommodate the possible confounding scenario of accruing a large majority of *FGFR* amplification only patients vs. mutations/fusions, we will stratify accrual, with planned enrollment of an equal number of *FGFR* amplification only and of *FGFR* mutation/fusion patients. Also, no more than 10 patients would be enrolled for a specific tumor type.

Decision Rule: The largest response rate where this treatment regimen would be considered ineffective in this population is 5%, and the smallest response rate that would warrant subsequent studies with this proposed regimen in this patient population is 20%. The following two-stage Simon minimax phase II study design requires a maximum of 30 evaluable patients to test the null hypothesis that the true response rate is at most 5%.

Constraining the Type I error rate to 5% and with at least 80% power, this two-stage Simon minimax study design will require 30 evaluable patients to test these hypotheses regarding the ORR with ponatinib in this patient population. As described above, to address possible confounding that could result from accruing a large majority of *FGFR* amplification only patients, a subpopulation that may not be as susceptible to the targeting of ponatinib, we will restrict accrual of the *FGFR* amplification only patients to 15, and accrue 15 patients identified as having *FGFR* mutations/fusions. No more than 10 patients would be enrolled for a single tumor type regardless of *FGFR* alteration.

Under this design, the first stage will enroll 10 evaluable patients. If we observe at least one response in the first stage, the study will proceed to the second stage and enroll an additional 20 evaluable patients. Given the expected greater prevalence rate of the *FGFR* amplifications, we expect that it is not unlikely that the first 10 patients accrued in this cohort will be all amplification only patients. If this is the case and no responses are observed, then we will consider this adequate early evidence that the regimen is not sufficiently active in the *FGFR* amplification only patients. At this point, we would keep accrual open, but only to the *FGFR* mutation/fusion patients. An interim decision rule would not be implemented in this subgroup of patients. If there are 0 responses in the first 10 all amplification patients, accrual of patients with *FGFR* amplifications would cease. Subsequently, 20 patients would be enrolled and enrollment would be restricted to patients with *FGFR* mutations and fusions.

In the final analysis, if we see at least 4 patients who have a response to treatment out of the 30 evaluable patients, we will consider this sufficient evidence that this combination regimen has promising activity in this patient population. Otherwise, if 3 or fewer patients have a response in the first 6 cycles of therapy, we will consider this regimen to not be sufficiently active in this population.

Analysis Plan: As described above, the proportion of responses for the purposes of this decision rule will be calculated out of all eligible patients who receive any treatment. Assuming the number of responses is binomially distributed, 95% binomial confidence intervals will also be calculated for the estimate of the proportion of responses.

Cohort B: KIT, PDGFR α , RET, FLT3, ABL1 alterations

Design Summary: As mentioned above, this cohort will consist of patients identified with rare gene targets for whom there may still be downstream targeting and efficacy associated with ponatinib; these patients will include those identified with *KIT*, *PDGFR α* , *RET*, *ABL1*, and *FLT3* alterations. Given the variable types of genetic alterations that may be accrued to this cohort in addition to the multiple disease types, this cohort will be a pilot evaluation without a corresponding formal decision rule. This cohort will be open to accrual for the timeframe that Cohort A is open to accrual, with up to a maximum of 15 patients being accrued to this cohort. Our analyses for this cohort will be largely exploratory and descriptive, focusing on identifying the composition of patients who enrolled to this cohort in terms of their genetic alteration and disease type along with biomarker evaluations and clinical outcomes. While this cohort does not have specific endpoints associated with it, it provides a mechanism to make ponatinib available to those with rare genetic alterations and collects valuable preliminary data for ponatinib single agent therapy in the various types of patients who may be enrolled.

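### The Cohort A rule (at least 1 of 10, then at least 4 of 30) is not the Simon minimax design it is called, and its exact type I error with the stage 1 stop applied is 5.13%, just above the stated 5%

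*Combined protocol and SAP*

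**What the plan says.** All of this is in Section 12.2 of the combined protocol and SAP, under Cohort A. The design is named three times: "This cohort will utilize a two-stage Simon minimax phase II study design"; in the Decision Rule paragraph, "The following two-stage Simon minimax phase II study design requires a maximum of 30 evaluable patients"; and in the paragraph after it, "Constraining the Type I error rate to 5% and with at least 80% power, this two-stage Simon minimax study design will require 30" evaluable patients. The null response rate is at most 5% and the rate of interest is 20%.

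On the stages, "the first stage will enroll 10 evaluable patients". At least one response leads to 20 more patients. Success is declared "if we see at least 4 patients who have a response to treatment out of the 30 evaluable patients", and 3 or fewer responses is failure.

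Accrual is split by type of alteration: "we will stratify accrual, with planned enrollment of an equal number of" amplification-only and mutation/fusion patients, 15 of each. There is one exception to the stage 1 stop. The plan expects that "it is not unlikely that the first 10 patients accrued in this cohort will be all amplification only patients". If that happens with no response, amplification accrual closes and 20 mutation/fusion patients follow; of these the plan says "An interim decision rule would not be implemented in this subgroup of patients".

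**The concern.** Minimax has a fixed meaning: among two-stage designs that meet the error limits, the one with the smallest maximum sample size. A reader who derives it from the plan's own inputs gets 27, not 30, and cannot tell whether the label, the sample size or the cut-off is at fault. The same sentence presents 5% as a limit that the design respects. Cohort B has no formal decision rule, so these are the only operating characteristics the trial claims. They should be true of the rule that will be applied, including the branch in which the stop is waived.

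**Working it through.** **Inputs (all Section 12.2).** p0 = 0.05, p1 = 0.20, type I error limit 5%, power at least 80%, n1 = 10, continue on at least 1 response, n = 30, success on at least 4. The test is one-sided, because the null is a rate of at most 5%.

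**1. The written rule with the stop applied.** The probability of success is the sum over x = 1 to 10 of P(Bin(10, p) = x) × P(Bin(20, p) ≥ 4 − x).

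| Stage 1 responses | p = 0.05 | p = 0.20 |
|---|---|---|
| 1 | 0.31512 × 0.07548 = 0.02379 | 0.26844 × 0.79392 = 0.21312 |
| 2 | 0.07463 × 0.26416 = 0.01972 | 0.30199 × 0.93082 = 0.28110 |
| 3 | 0.01048 × 0.64151 = 0.00672 | 0.20133 × 0.98847 = 0.19901 |
| 4 or more | 0.00103 | 0.12087 |
| **Total (from unrounded terms)** | **0.05125** | **0.81409** |

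Type I error is 5.13% against a stated 5%. Power is 81.4% against a stated 80% or more. The chance of an early stop at p = 0.05 is 0.95^10 = 0.59874, so the expected sample size is 10 + 20 × 0.40126 = 18.0.

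**2. The designs the name could refer to.** All two-stage designs with type I error at most 5% and power at least 80% were enumerated. None has a maximum of 26 or fewer.

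| Design | Stage 1 | Final | Type I error | Power | Expected N at 5% |
|---|---|---|---|---|---|
| Simon minimax | ≥1 of 13 | ≥4 of 27 | 4.16% | 80.1% | 19.8 |
| Simon optimal | ≥1 of 10 | ≥4 of 29 | 4.68% | 80.1% | 17.6 |
| As written | ≥1 of 10 | ≥4 of 30 | 5.13% | 81.4% | 18.0 |

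The written rule has the optimal design's first stage and cut-off with one patient added. That patient moves the type I error from 4.68% to 5.13%. Relaxing the type I limit to 6% at 80% power still gives a minimax maximum of 27, so rounding does not rescue the label.

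**3. The waiver, with one response rate in all patients and the 4 of 30 cut-off kept.** It adds the path of 0 of 10 followed by at least 4 of 20.

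- At 5%: 0.59874 × 0.01590 = 0.00952. Type I error is at most 0.05125 + 0.00952 = 0.06077.
- At 20%: 0.10737 × 0.58855 = 0.06320. Power is at most 0.81409 + 0.06320 = 0.87729.

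These are the values if the first 10 patients are certain to be all amplification-only. If that has probability q, the increments are 0.95q and 6.3q percentage points. The documents give no q. Assuming independent accrual with amplification-only share s, q = s^10. Then s = 0.8 gives q = 0.107, type I error 5.2% and power 82.1%; s = 0.9 gives q = 0.349, 5.5% and 83.6%.

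**4. The waiver with unequal response rates.** Suppose, as an assumption, that the null is a 5% average over the planned 15 and 15, and that the first 10 patients are all amplification-only. After at least one response, 5 amplification-only and 15 mutation/fusion patients follow; after none, 20 mutation/fusion patients follow.

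- Rates of 2% (amplification-only) and 8% (mutation/fusion): 0.0577 through the waiver + 0.0291 otherwise = 0.0868, or 8.7%.
- Rates of 0% and 10%: P(Bin(20, 0.10) ≥ 4) = 0.133, or 13.3%.

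The 6.1% is therefore a bound only when the rate is the same in both strata.

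**The case against.** The plan gives its limit as a whole percent, and 5.125% rounds to 5%. Power exceeds 80%, a total of 30 fits equal strata of 15 where 29 cannot, and the rule is explicit enough to apply without a name. The waiver is disclosed, so the missing figures for it are an omission and not a miscalculation. The documents give no probability for the composition that triggers it and do not expressly restate the 4 of 30 cut-off for that branch.

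Most of this stands, and it keeps the point minor. It does not save the label, because 27 patients meet both limits. Nor does it make 5% a constraint that the rule satisfies: the documents never link the choice of 30 to the strata or give the error rate that results, and the waiver can only move that rate up.

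A reader might also infer that 6.1% is the worst case for this design. The documents do not support that. Section 12.2 itself expects amplification-only patients to be less susceptible to the drug, and the bound fails under that kind of difference. Nor can 8.7% or 13.3% be read as the trial's type I error: they rest on assumed rates and on a definition of the null that the plan does not give.

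**Conclusion.** Wrong as written, and minor. The rule is not Simon minimax; it is the Simon optimal design plus one patient. With the stop applied, the exact type I error is 5.13%, which is 0.13 points over the stated limit, and the power is 81.4%, which meets the claim. Those figures need only the plan's own inputs and a common response rate. The waiver raises the type I error further by an amount that depends on accrual: at most 6.1%, with power at most 87.7%, given the same rate in all patients and the 4 of 30 cut-off.

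It would be a mistake to conclude that the trial is underpowered, that its error control has failed materially, or that it should be redesigned at 27 patients. Power is above target, the excess with the stop applied is within whole-percent rounding, and the equal-strata plan is a plausible reason for 30, although the documents do not give it as the reason.

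**What to change.** In Section 12.2, Cohort A, delete the words Simon minimax from the opening sentence and from the Decision Rule paragraph. In the next paragraph, replace the first sentence, which carries the third use of the label and the 5% constraint, with:

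> This two-stage design (stage 1: 10 evaluable patients, continue on at least 1 response; total 30 evaluable patients, success on at least 4 responses) tests a true ORR of at most 5% against 20%, with exact type I error 5.1% and power 81.4% when the stage 1 stop is applied. If the stop is waived because the first 10 patients are all amplification-only, and the final cut-off of at least 4 of 30 is kept, then with the same response rate in all patients the type I error is at most 6.1% (5% rate) and power at most 87.7% (20% rate); these bounds do not hold if response rates differ between amplification-only and mutation/fusion patients.

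The cost is two deletions and one replaced sentence. The decision rule, cut-offs and patient numbers do not change. The only downside is a stated type I error slightly less favourable than 5%.

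### Cohort A: if 0/10 closes the amplification-only group, a later success would still be worded for the whole cohort, and the stated 5% type I error does not describe that path (6.1%).

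*Combined protocol and SAP*

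**What the plan says.** Section 12.2 sets a two-stage rule for Cohort A, with a null response rate of 5% and a target of 20%. The first stage has 10 patients, and at least one response leads to 20 more. The stated properties are: "Constraining the Type I error rate to 5% and with at least 80% power". The intended mix is 15 amplification-only and 15 mutation/fusion patients.

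The section then adds a special path. Because amplifications are expected to be more common, "we expect that it is not unlikely that the first 10 patients accrued in this cohort will be all amplification only patients". If those 10 show no response, "then we will consider this adequate early evidence that the regimen is not sufficiently active in the" amplification-only patients. Accrual of that subgroup ends, and the plan goes on: "Subsequently, 20 patients would be enrolled and enrollment would be restricted to patients with" alterations of the other two kinds, mutation or fusion. For these 20 the plan says: "An interim decision rule would not be implemented in this subgroup of patients".

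One final rule follows for every path: "if we see at least 4 patients who have a response to treatment out of the 30 evaluable patients, we will consider this sufficient". The conclusion attached to reaching that count is worded as "evidence that this combination regimen has promising activity in this patient population". On the denominator, "the proportion of responses for the purposes of this decision rule will be calculated out of all eligible patients who receive any treatment".

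Response by alteration type is a secondary objective in Section 1.2. Section 12.4 describes no analysis for it.

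**The concern.** On this path the plan draws two conclusions that overlap. It first finds amplification-only tumours insufficiently responsive. It then keeps a success statement whose population, Cohort A, includes those tumours. Nothing in Section 12.2 limits the statement, and no mutation/fusion rate, interval or conclusion is specified for the branch.

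Continuing after 0/10 also gives the cohort a second route to success. The error rates quoted for a two-stage design assume that 0/10 ends it. At stake are who a positive result is about and whether the type I error reported with it is correct.

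**Working it through.** **Inputs, all from Section 12.2:** null 5%; target 20%; 10 patients then 20; success at 4 or more of 30; in the branch, 20 mutation/fusion patients after 0/10 in amplification-only patients. I assume that 0/10 in a mixed first stage stops the cohort, as the basic rule implies.

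**1. The plan's own figures.** If 0/10 always stops the cohort:

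P(success) = Σ over x = 1 to 10 of P(Bin(10,p) = x) × P(Bin(20,p) ≥ 4 − x).

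- p = 0.05: 0.0513. The stated 5% is slightly exceeded.
- p = 0.20: 0.8141. The stated power of at least 80% is reproduced.

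**2. Added by continuing after 0/10, when the first 10 are all amplification-only and both subgroups share one rate p.** The extra term is (1 − p)^10 × P(Bin(20,p) ≥ 4).

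- p = 0.05: 0.95^10 × 0.0159 = 0.5987 × 0.0159 = 0.0095. Total 0.0513 + 0.0095 = 0.0608.
- p = 0.20: 0.80^10 × 0.5886 = 0.1074 × 0.5886 = 0.0632. Total 0.8141 + 0.0632 = 0.8773.

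As a check, with a common rate and no stop at 0/10 the procedure reduces to a single-stage rule of at least 4/30. P(Bin(30,p) ≥ 4) is 0.0608 at 5% and 0.8773 at 20%, which agrees.

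**3. Conditional on the branch.** The 10 zeros are fixed, so the rule is at least 4/20 in mutation/fusion patients. P(Bin(20,p) ≥ 4) is 1.6% at 5%, 58.9% at 20%, 77.5% at 25% and 89.3% at 30%.

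**4. How often this arises.** The documents give no amplification share s, so the values below are assumptions, with patients arriving independently. Branch entry is s^10 × 0.5987, taking a 5% response rate in amplification-only patients. Averaged type I error is 0.0513 + s^10 × 0.0095.

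| Assumed s | First 10 all amplification-only | Branch entered | Averaged type I error |
|---|---|---|---|
| 70% | 2.8% | 1.7% | 5.2% |
| 80% | 10.7% | 6.4% | 5.2% |
| 90% | 34.9% | 20.9% | 5.5% |
| 95% | 59.9% | 35.8% | 5.7% |

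**5. What would be reported.** In the branch the expected pooled rate is 20 × pm / 30, two thirds of the mutation/fusion rate pm. With 4 responses (exact 95% intervals):

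- mutation/fusion: 4/20 = 20.0% (5.7% to 43.7%);
- amplification-only: 0/10 (0% to 30.8%);
- pooled: 4/30 = 13.3% (3.8% to 30.7%).

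**6. Other cutoffs in the branch, overall type I error on this path.**

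- At least 3/20: 0.0513 + 0.5987 × 0.0755 = 0.0964 (9.6%, from unrounded terms).
- At least 5/20: 0.0513 + 0.5987 × 0.0026 = 0.0528 (5.3%), with conditional power at 20% falling to 37.0%.

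**The case against.** The case on the other side is substantial, and most of it stands.

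- The plan does record the negative judgement on amplification-only patients, and Section 1.2 makes response by alteration type a secondary objective. A careful reader would probably not apply a later positive verdict to the closed subgroup. This narrows the gap but does not close it: the final rule has no exception, and Section 12.4 does not plan the subgroup rates.
- A reader might infer that pooling distorts the primary response rate and that the denominator must become 20. The documents do not support that. The endpoint is the response rate of Cohort A, which includes amplifications by definition. The ordinary path has 15 amplification-only patients among 30; this branch has 10. Section 12.5.2 also bases conclusions on all eligible patients. Which rate to headline is a choice on which statisticians may differ.
- A reader might also hold against the branch that the interval for 4/30 includes 5%. That is true of a minimum success on every path, so the branch does not cause it.
- The 58.9% might be read as a failed power claim. It is conditional on the branch. The plan's claim concerns the whole procedure, where power at a common 20% is 87.7%.
- The excess type I error is small, and the likelihood of the branch rests on assumed shares. The plan's remark about likelihood concerns only an all-amplification first 10; the branch also needs no responses among them.

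**Conclusion.** The point holds in a limited form. Followed as written, Section 12.2 would attach a positive conclusion to a population that includes a subgroup the plan has already found insufficiently responsive, although only the other 20 patients could have produced the success.

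The stated type I error is also not right for this path: 6.1% if the first 10 are all amplification-only, against 5.1% for the basic two-stage rule and 5% as stated. Averaged over assumed shares of 70% to 95% it is about 5.2% to 5.7%. These figures take a true rate of 5% in both subgroups, exact binomial responses, and stopping after 0/10 in a mixed first stage.

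The pass/fail result is unaffected, the claim of at least 80% power survives at a common 20%, and continuing accrual is not itself at fault.

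**What to change.** Add a paragraph to Section 12.2 stating that, in this branch:

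- any conclusion of promising activity applies to FGFR mutation/fusion patients only, and amplification-only patients are reported as not sufficiently responsive (0/10);
- the mutation/fusion rate x/20 and the amplification-only rate 0/10, each with its exact 95% interval, are pre-specified and reported beside the pooled x/30, with a note that the pooled rate is expected to be two thirds of the mutation/fusion rate;
- type I error is 5.1% for the basic two-stage rule and about 6.1% on this path, with the conditional figures for the branch (type I error 1.6%; power 58.9% at 20%, 77.5% at 25%, 89.3% at 30%);
- the cutoff stays at 4 responses, since 3 raises the error on this path to 9.6% and 5 gains little for a large loss of power.

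Every eligible treated patient stays in the analysis, so Sections 12.1(a) and 12.5.2 need no redefinition. The headline rate is the sponsor's choice.

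The cost is a few sentences, with no extra patients and no change in the decision. The stated type I error becomes slightly less favourable and a positive conclusion narrower.
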